10.4. Secondary analyses

Our secondary analyses consist of the same analytical approach as the primary analysis but with outcome measures replaced with our four secondary outcomes: financial security, subjective wellbeing, life satisfaction and employment.

10.5. Sub-group Analyses

We hypothesise that participation may disproportionately benefit those who would either otherwise have low levels of the outcomes or high levels of the outcome.

Because baseline outcomes are not a perfect predictor of endline outcomes, instead of doing traditional subgroup analyses based on baseline characteristics or levels of the outcomes at baseline, we will instead conduct quantile regressions, allowing us to evaluate the impact on the outcomes at the 25th and 75th percentiles of the outcomes at endline. This analytical specification will be identical to that of the main analyses, but change the point in the distribution at which outcomes are evaluated, and with standard errors generated by Stata 17 for quantile regressions.

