9. SAMPLE SIZE AND POWER CALCULATION

9.1. Sample Size / Power Calculation

Sample size is limited by the availability of funding to deliver the personalised budgets. We therefore provide the power implications of various attrition scenarios between baseline and a single endline (i.e. the 12-month follow-up).

Under our likely attrition scenario of 25%, our minimum detectable effect size (MDES) at alpha = 0.05 and beta = 0.8 is 0.273, representing a moderate effect size. Owing to the costly nature of the intervention and effect sizes observed in similar studies, we believe this is acceptable.

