10.3. Primary Analyses

Analytical approach

Our main analytical approach for our primary analysis is regression analysis, which will be conducted on an intention-to-treat, complete cases basis. For our main housing outcomes, housing stability and perceived housing quality and satisfaction, measured via Residential Time Line Follow Back Inventory and the OMRA tool, we will conduct a linear regression, evaluated at the mean. Formally, this will be an autoregressive (AR-1), model, specified as:

$$Y_{ipt} = \alpha + \beta_1 Y_{ip0} + \beta_2 B_i + \beta_3 X_i + \beta_4 P_p + u_i$$

Where:

 Y_{ipt} is the value of the respective outcome measure (housing stability and perceived housing quality and satisfaction), for participant i at time t (endline in the primary analysis), referred by charity partner p.

 α is a regression constant

 Y_{i0} is the baseline value of the outcome for participant i in charity partner p.

 B_i is a binary treatment indicator set to 1 if participants are treated and zero else.

 X_i is a vector of participant demographic characteristics including gender (operationalised as a trinary variable) and age (operationalised as a categorical variable with 7 values including prefer not to say).

 P_p is a vector of charity partner fixed effects, reflecting that charity partner is a stratification variable.

 u_i is an error term.

This analysis will be conducted with two values of the time indicator, at the midline and endline data collection points, in both cases using the baseline data at time 0 as a control. Uncertainty will be reported through confidence intervals at p-values. We will report the binary indicator of whether the treatment effect is statistically significant, as well as present the p-value continuously and the confidence intervals.

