10.7. Exploratory analyses

Following discussions with Greater Change, we are interested in whether effects are concentrated elsewhere in the distribution from the mean of our outcome measures. For example, it is hypothesised either that people with higher than average housing stability might benefit from the intervention, or that people with lower housing stability might do so. However, these hypotheses are not sufficiently well articulated at this stage to form a part of the Theory of Change, or to specify which has the larger effect. To investigate these hypotheses, we will conduct quantile regressions specified in the same way as our main analyses, evaluating the impact of the intervention at the 25th and 75th percentile.

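### Sections 10.5 and 10.7 ask whether one part of the outcome distribution benefits more than another, but specify only separate effects at the 25th and 75th percentiles and no estimate of their difference

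*Protocol*

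**What the plan says.** Protocol section 10.5 (Sub-group Analyses) opens with a two-way hypothesis: "We hypothesise that participation may disproportionately benefit those who would either otherwise have low levels of the outcomes or high levels of the outcome". In place of baseline subgroups it plans quantile regressions, "allowing us to evaluate the impact on the outcomes at the 25th and 75th percentiles of the outcomes at endline". The model is carried over: "This analytical specification will be identical to that of the main analyses, but change the point in the distribution at which outcomes are evaluated".

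Section 10.7 (Exploratory analyses) returns to the same analysis. Its aim is that "we are interested in whether effects are concentrated elsewhere in the distribution from the mean of our outcome measures". On which of the two ideas carries the greater impact, it concedes that "these hypotheses are not sufficiently well articulated at this stage to form a part of the Theory of Change, or to specify which has the" (the quotation stops just short of the sentence's end), and again plans quantile regressions, "evaluating the impact of the intervention at the 25th and 75th percentile".

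For the main analyses, section 10.3 says: "We will report the binary indicator of whether the treatment effect is statistically significant". The same sentence adds the p-value on its continuous scale and the confidence interval.

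Neither 10.5 nor 10.7 compares the two quantile effects with each other or with the mean effect, and neither gives a rule for calling an effect concentrated.

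**The concern.** The question is about a difference between effects, while the planned output is two effects side by side. An estimate at each percentile, even with its own confidence interval, is not an estimate of the gap. The two estimates come from the same participants and are correlated, so the gap's interval cannot be read off the two separate ones.

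The practical risk lies in how such output tends to be read. If one percentile reaches significance and the other does not, it is easy to conclude that the benefit sits at that end. That pattern is common when the effect is the same throughout. Because the hypothesis runs in both directions, either discordant pattern could be taken to support it. What is at stake is a statement in the report that people with low (or high) housing stability gain more, when the data show no such thing.

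**Working it through.** **Inputs.** Table 7 and sections 9.1 and 9.2 give 360 randomised 1:1, 25% attrition and so N = 270, a baseline-endline correlation of 0.6, and two-sided alpha 0.05. Section 9.1 states that "our minimum detectable effect size (MDES) at alpha = 0.05 and beta = 0.8 is 0.273"; the 0.8 printed as beta is the power, as Table 7 shows. Assumed here and not given in the protocol: normal residuals, and a treatment effect that shifts everyone equally. Partner and demographic covariates are left out.

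**Step 1: reproduce the plan's own figure.** The residual SD is sqrt(1 − 0.6²) = 0.8.
MDES = (1.960 + 0.842) × 0.8 × sqrt(4/N).
- N = 360: 0.2363 (stated 0.236)
- N = 270: 0.2728 (stated 0.273)
- N = 234: 0.2930 (stated 0.293)

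All three reproduce.

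**Step 2: precision of one quantile effect.** With normal errors, the variance relative to the mean effect is 0.25 × 0.75 / φ(z₀.₂₅)² = 1.857. At N = 270:
SE = 0.8 × sqrt(4/270) × sqrt(1.857) = 0.133 SD.
The correlation between the 25th and 75th percentile estimates is (0.25 × 0.25)/(0.25 × 0.75) = 1/3.

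**Step 3: a uniform effect equal to the MDES.** The expected z at each percentile is 0.273/0.1327 = 2.06, so each test has about 54% power. From the bivariate normal with correlation 1/3, both are significant in 34% of trials, neither in 27% and exactly one in 39%. Simulated quantile regressions with baseline adjustment (1,500 trials, N = 270) gave 31%, 28% and 41%. Some fits hit the iteration limit, but the results agree with the formula. At N = 360 and N = 234, each at its own MDES, the formula also gives 39% (simulations 37% and 39%).

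**Step 4: range of uniform effects at N = 270.**

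| Uniform effect (SD) | Power at each percentile | Exactly one significant |
|---|---|---|
| 0 | 5% | 9% |
| 0.15 | 20% | 27% |
| 0.20 | 33% | 35% |
| 0.273 | 54% | 39% |
| 0.35 | 75% | 30% |
| 0.40 | 85% | 21% |
| 0.50 | 97% | 6% |

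The curve peaks when each test has 50% power, where the value is 2 × [0.5 − (0.25 + arcsin(1/3)/2π)] = 39.2%. The MDES falls almost exactly there. These figures are per outcome.

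**Step 5: the direct contrast.** The SE of the 75th-minus-25th difference is 0.1327 × sqrt(2 × (1 − 1/3)) = 0.153 SD. Under a uniform effect it is significant at about the nominal 5%; a small bootstrap check of 150 trials gave 4.7%. For 80% power the true gap must be (1.960 + 0.842) × 0.1532 = 0.43 SD (0.37 at N = 360, 0.46 at N = 234). A gap of 0.273 SD has about 43% power.

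**The case against.** The strongest reply is that this is an omission in a non-primary analysis, that an analysis plan not shown here could supply the contrast, and that nothing in 10.5 or 10.7 is wrong as stated. That limits the weight of the point but does not remove it. The protocol does not defer on this matter: it fixes the model, the two percentiles and the software, and what it fixes does not address the question asked.

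Several further objections stand:

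- A reader might infer that the plan will declare concentration whenever only one percentile is significant. No such rule is written. Section 10.5 speaks of evaluating the impact, and the identical specification may mean only the regression equation. Even if the reporting rule of 10.3 carries over, it also requires p-values and confidence intervals.
- A reader might take 39% as the general rate. It is the top of the curve, and the rate is small for large effects.
- A reader might see a contradiction in evidential status between 10.5 and 10.7. Neither section claims a confirmatory test; this is mostly duplicated text under two headings.
- The contrast is not a universal remedy. Employment is a categorical status (section 7.2, Annex F) with no useful 25th and 75th percentile effects. Days in secure accommodation are bounded at 0 and 360 (section 7.1). If the 75th percentile sits at 360 in both arms, its effect is zero by construction, and a uniform underlying shift would produce a difference from the ceiling alone. A tail contrast also misses the case in 10.7 where both tails differ equally from the mean.
- The protocol does not say that quantile results will decide who receives later budgets, so that consequence is conjecture.

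**Conclusion.** The point holds in a limited form. Sections 10.5 and 10.7 ask a comparative question and specify no comparative estimate. If the results are read by which percentile is significant, a uniform effect of 0.15 to 0.40 SD would look concentrated at one end in about 21% to 39% of trials at N = 270, peaking near the MDES and falling to 6% at 0.50 SD. This rests on normal errors, a pure location shift and the Table 7 inputs; bounded days data could behave differently, and no range over distribution shape was computed. The documents do not support saying that the plan prescribes a faulty decision rule. The analysis is not primary and 10.7 calls it exploratory, so this is a worthwhile, inexpensive correction and does not threaten the trial's main conclusions.

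**What to change.** - For the continuous or scale outcomes, and not for employment, add the 75th-minus-25th percentile difference in treatment effect at endline, with a 95% CI from a joint bootstrap fit (iqreg, or sqreg followed by a test of equal coefficients, in the Stata already named in 10.5).
- Base any statement of disproportionate benefit on that difference, and not on which percentile is significant.
- Report the two quantile effects with CIs next to the mean effect, so that the comparison with the mean raised in 10.7 is visible.
- For days in secure accommodation, first check whether either percentile lies at 0 or 360. If so, do not interpret the contrast as heterogeneity.
- Describe the analysis once, as exploratory, by merging 10.5 into 10.7.
- State the low power in advance: SE about 0.153 SD at N = 270, and a gap of about 0.43 SD needed for 80% power.

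The cost is one paragraph and one extra command, with no new data. The drawback is that a true but moderate difference will often go undetected, so a non-significant contrast must not be reported as evidence that the effect is uniform.

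### The quantile regressions in sections 10.5 and 10.7 estimate effects given baseline, demographics and partner, not effects at the 25th and 75th percentiles of the endline outcome

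*Protocol*

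**What the plan says.** Protocol section 10.5 hypothesises that "participation may disproportionately benefit those who would either otherwise have low levels of the outcomes or high levels of the outcome". It notes that baseline predicts endline only imperfectly. For that reason it chooses quantile regression "instead of doing traditional subgroup analyses based on baseline characteristics or levels of the outcomes at baseline", and describes the result as "allowing us to evaluate the impact on the outcomes at the 25th and 75th percentiles of the outcomes at endline".

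The same section then fixes the model: "This analytical specification will be identical to that of the main analyses". Section 10.3 defines that main model as a regression of the endline outcome on the baseline outcome, the treatment indicator, gender, age and charity-partner fixed effects, "in both cases using the baseline data at time 0 as a control". It has no treatment interaction.

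Section 10.7 presents the same analysis as exploratory: "we will conduct quantile regressions specified in the same way as our main analyses", again at the 25th and 75th percentiles. Neither section states a rank-invariance assumption.

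**The concern.** Section 10.5 asks about people ranked by the endline outcome they would have had without the intervention. A quantile regression with the baseline outcome as a regressor ranks people differently: it asks who does worse or better than their own baseline, demographics and partner predict. Someone at the conditional 25th percentile may be doing well overall. The description in 10.5 and the fixed specification therefore refer to different quantities.

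A second gap applies to any quantile effect. It compares two outcome distributions. Reading it as the effect on people who would otherwise be low or high requires that treatment leaves people's ranks unchanged (rank invariance).

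These regressions are the only planned analysis of who benefits. As specified, they could be reported as showing no difference in who benefits when the difference is large.

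**Working it through.** **Inputs.** Pre/post correlation 0.6, two-sided alpha 0.05, power 0.8, and effective sample sizes 360, 270 and 234 (section 9, Table 7). Section 9.1 gives the minimum detectable effect for 25% attrition as "at alpha = 0.05 and beta = 0.8 is 0.273". Allocation is 1:1 (section 5.2).

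**The protocol's own figures.** MDES = (1.960 + 0.842) × √(1 − 0.6²) × √(4/N).
- N = 360: 0.2363 (stated 0.236)
- N = 270: 0.2728 (stated 0.273)
- N = 234: 0.2930 (stated 0.293)

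All three reproduce and are not in dispute. The value 0.273 sets the scale below.

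**Why the planned model is nearly blind to baseline-related benefit.** Suppose the effect depends only on baseline, e(b). At a fixed baseline b, treatment shifts the whole outcome distribution by e(b), so the conditional effect at b is the same at the 25th and 75th percentiles. With no interaction, each fit averages e(b) over baseline, and both coefficients land near the mean effect.

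**Simulation.** Standard normal baseline, endline correlation 0.6, 1:1 allocation, large samples (100,000 to 200,000). Gender, age and partner were left out. In the first two rows the effect is 0.546 SD in one half of the baseline distribution and 0 in the other, so the average is 0.546 / 2 = 0.273. Ranges cover repeated runs. The two right-hand columns give the 25th / 75th percentile effect in SD.

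| Who benefits | True mean effect, lowest / highest quarter of untreated endline | Planned model | Unconditional |
|---|---|---|---|
| Low-baseline half | 0.45 / 0.10 | 0.26–0.27 / 0.28–0.29 | 0.33–0.35 / 0.20–0.22 |
| High-baseline half | 0.10 / 0.44 | 0.27 / 0.29 | 0.11–0.15 / 0.41 |
| Everyone, 0.273 | 0.273 / 0.273 | 0.28 / 0.27 | 0.273 / 0.273 (pure shift) |
| Untreated endline below median, 0.546 | 0.55 / 0 | 0.41 / 0.14 | 0.54 / 0.01 |

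The first three rows are different answers to the protocol's question, yet the planned model's output barely differs between them.

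**Sensitivity, low-baseline benefit.** A correlation of 0.3 gives 0.26 / 0.28 and 0.8 gives 0.25 / 0.28. With 1.0 SD in the low half (correlation 0.6), the planned model gives 0.46 / 0.55, which leans the wrong way.

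**At n = 270** (400 runs), the mean 25th-minus-75th difference is −0.02 (SD 0.17) for low-baseline benefit and −0.01 (SD 0.15) for a uniform effect. The two cannot be told apart.

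**Rank invariance.** Let individual effects have mean 0.273 and SD 0.6, unrelated to the untreated outcome, so neither low nor high people gain more.
- Planned model: residual SD is 0.8 in control and √(0.64 + 0.36) = 1.0 in treatment. Effects are 0.273 ∓ 0.674 × 0.2 = 0.14 / 0.41.
- Unconditional: SD is 1 in control and √(1 + 0.36) = 1.166 in treatment. Effects are 0.273 ∓ 0.674 × 0.166 = 0.16 / 0.38.

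Both show a gradient that says nothing about who benefits, so removing the covariates does not remove the need for the assumption.

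**Interaction for comparison.** A treatment-by-baseline-half interaction recovers about 0.54 under low-baseline benefit, with about 73% power at n = 270. When benefit follows the untreated endline outcome instead, it gives 0.38 / 0.16, about as attenuated as the planned model.

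**The case against.** The strongest reply is that 10.5 asks about the endline level people would otherwise have, not about baseline, and declines baseline subgroups for a stated and true reason. When benefit follows the untreated endline outcome directly, the planned model points the right way, and a baseline interaction does no better. That stands. A reader might infer that quantile regression cannot address the question, or that a baseline interaction should replace it. The fourth row of the table supports neither: unconditional quantiles come closest there. The reply does not rescue the specification, because having declined baseline as the grouping variable, the plan then conditions on it.

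A reader might also infer that, for days in secure accommodation, the planned 25th-percentile effect is zero by construction because participants start in temporary accommodation. The protocol does not support that. It gives no distribution of days, and its account of the outcome (section 7.1, Annex B) does not say which housing categories count as secure. With baseline in the model, more than a quarter of zeros in each arm also does not force a zero coefficient. With assumed zero shares of 40% v 28%, the conditional effect came out at about 14 days in one simulation and 0 in another, depending on how baseline was modelled. It was 0 at 60% v 45% and 50% v 35%.

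Finally, this is a subgroup analysis that section 10.7 itself labels exploratory, and an interaction at n = 270 would often miss a smaller gradient. Both points limit the weight of the concern. Neither corrects the mismatch.

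**Conclusion.** The point holds in a limited form. What 10.5 says the regressions estimate, and what the specification fixed in 10.5 and 10.7 does estimate, are different quantities. Under baseline-related benefit averaging 0.273 SD, the planned model returns about 0.26 to 0.29 at both percentiles whichever half benefits, while the true mean effects in the lowest and highest quarters of untreated outcome differ by about 0.35 SD (0.45 − 0.10). Under benefit tied directly to the untreated endline outcome it is informative but attenuated: a contrast of 0.41 − 0.14 = 0.27 against 0.55.

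The sizes rest on a normal outcome, correlation 0.6, all-or-nothing effects, and omission of gender, age and partner. They were not derived for a bounded day count. The mismatch itself needs none of these assumptions. The matter is minor to moderate: worth correcting before analysis, with no bearing on the primary estimate.

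**What to change.** In sections 10.5 and 10.7:

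- Estimate unconditional quantile treatment effects at the 25th and 75th percentiles, with arm and randomisation strata only, or with an unconditional method that uses covariates for precision alone (for example, recentred influence function regression). Partner dummies in an ordinary quantile regression still condition on partner, so the second route matches the wording of 10.5 more closely.
- Describe the results as effects on the outcome distribution. Interpret them as effects on people who would otherwise be low or high only under a stated rank-invariance assumption.
- Add, without substituting it, a pre-specified treatment-by-baseline-outcome interaction in the linear model, and say that it is imprecise at n = 270.
- For days in secure accommodation, also report the proportion in each arm with any secure days. If more than a quarter of both arms have none, both lower quartiles are zero and the unconditional 25th-percentile difference is zero whatever happens elsewhere. Whether that will occur is unknown.

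The cost is a change of estimator, one added model per outcome, one added proportion and some rewording. All the data are already being collected.

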10.6. Sensitivity Analysis

Complementary to the main model, the following sensitivity analyses will be conducted to determine the robustness of the obtained results.

Non-Compliance

During implementation of the intervention, it emerged that some participants in the intervention group spent their personal budgets in a way that deviated from the plan agreed with Greater Change and their Charity Partners. Although some deviations were minor (spending in one shop rather than another), some were more substantial.

In order to address this, participants receiving the intervention will be treated as non-compliant in any instance where;

- No amount is agreed
- An amount is agreed but is not spent
- An amount is agreed and spent, but what was purchased differed substantially from what was intended. In order to do this:
- All cases where any deviation, including minor ones, occurred will be provided by Greater Change to the evaluator.
- A "substantial" deviation will be determined by the evaluator in consultation with the Centre for Homelessness Impact.
 Conditions to establishing whether a deviation is substantial will include:
 - An increase in spending on an item within the same 'class' of spending of more than 50% (and an equivalent reduction in spending in another class), and where total amount of money misspent in this way is more than £500.
 - A case where money is spent on a different "class" of spending than was agreed entirely.
 - A case where fraud or deception on the part of the participant or charity partner is suspected.

As an additional robustness check, we will treat these additional non-compliant participants as compliant (as they would be in the per-protocol analysis) to determine the effect, if any, of their being classed as non-compliant on the estimated impact of the intervention.

CACE Analysis

In order to monitor compliance, a binary variable will be generated, taking the value of 1 if the individual complied with the randomisation protocol and 0 otherwise. For compliance levels lower than the specified threshold, a specific Complier Average Causal Effect (CACE) will be estimated using the instrumental variable (IV) approach with the two-stage least squares method.

First, treatment received by participants, specified by \boldsymbol{d}_i is regressed on the instrumental variable \boldsymbol{B}_i of participants randomised to treatment.

$$d_i = 1{\{\gamma_0 + \gamma_1 B_i + e_i > 0\}}$$

Where 1{.} is an indicator function that is equal to 1 if its argument is true and 0 otherwise.

Then the outcome variable is regressed on $E(d_i|B_i)$ with an OLS regression of the form:

$$Y_{ipt} = \alpha + \beta_1 Y_{ip0} + \beta_2 E(d_i | B_i) + \beta_3 X_i + \beta_4 P_p + u_i$$

Where the CACE estimator is β_2

Outcome imputation

We anticipate attrition between baseline, midline and endline data analysis. We will conduct missing data analysis as described below in 10.9, but given that every participant will complete the baseline survey, we primarily expect attrition in terms of outcomes, which will not be imputed under the missing data analysis. However, we will include sensitivity analysis which imputes outcomes between the two post-treatment data points where participants have missing data for one of these points but not the other. As such, if someone is missing data from midline but completes the endline data collection, we will impute their midline outcome measure as their endline outcome, and vice versa.

If exploratory analysis of the missingness mechanism satisfies the MAR assumption, the imputation of these points will be conducted with a dataset that incorporates all three time points to allow for the maximisation of all observed information in the process of imputation.

Following imputation, analysis will be conducted as previously described, for each post-treatment time point separately.

 For the main analyses, our primary outcome measure will be how many days out of the 360 after randomisation that a person is in secure accommodation. This measure will combine the measurement

taken at six months (midline) and that at 12 months, each of which will capture the prior 180 days. When someone completes the endline data but not the midline, they will be asked to recall the last 360 days. As a sensitivity analysis, we will conduct analysis just using the 180 days prior to the endline data collection as an outcome measure.

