What (procedures)	Participants are referred to Greater Change via a referral form. A discussion takes place between the caseworker, Greater Change, and the participant to decide the best use of the personalised budget. When this is agreed, Greater Change will transfer the budget to the partner charity within 4 weeks, who will spend the money as agreed.
Who (provider)	The intervention will be delivered by Greater Change, in partnership with charity partners.
	•

-

² BMJ 2014;348:g1687; doi: https://doi.org/10.1136/bmj.g1687

How (format)	Money agreed will be transferred to the charity partner's bank account and used to purchase what was agreed.		
Where (location)	Across England: South West (Second Step), South East (Porchlight, Gravesham Council), London (Centre Point Soho, Depaul UK, Your Place, Islington Council) Cambridge (Cambridge Cyrenians), East Midlands (Action Homeless), Leeds (Turning Lives Around)		
When and how much (dosage)	Payments will be made within 4 weeks of being agreed. It is anticipated that average payments will be around £4,000, but they may exceed this where necessary.		
	Participants are expected to spend their allocated funds within a three-month period. However, on a case-by-case basis, participants may receive extensions to ensure they can spend the funding as needed.		
Tailoring	Greater Change instructs charity partners to centre the personalised budget planning conversation around the participant's individual aspirations, goals and requirements and prompts caseworkers to afford their clients the dignity to make their own decisions. The decisions about spending are tailored to the individual circumstances of the participant, and are agreed upon by the charity partner; the participant; and Greater Change.		
Control condition	Control participants, as with treatment-arm participants, continue to be able to access all other support that they are entitled to (e.g. Universal Credit, rent assistance) and will not have been informed about the quantum of the personalised budget they could have received but have not due to their group allocation. This means, that control participants will not be allocated a personalised budget but are entitled to all otherwise available support.		

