The organisation delivering the model is Greater Change. They work together with local partner charities to ensure that clients receive additional non-financial support alongside funding in a timely manner. In contrast to other conditional funds, Greater Change does not have pre-set eligibility and spending criteria. The conditional funds are used to support the flexible and sustainable plan created and agreed upon ahead of time by the support worker and the service user.

This project will compare the use of personalised budgets that are managed by a caseworker and control groups under business-as-usual.

We assume that, on average, participants in the treatment group will receive funds of £4,000.

Participants are expected to spend their allocated funds within a three-month period. However, on a case-by-case basis, participants will be permitted to receive the intervention even in the face of necessary spending extensions, these cases will not be treated as non-compliant nor excluded from analysis. These extensions are in response to operational realities and are critical to the successful running of the trial. They also enable the intervention to more closely reflect how it would operate outside a trial context. The reasons for granting extensions can be grouped into two categories:

- Staff-related delays: including administrative expenditure delays, annual leave of case workers, and reduced partner engagement with participants.
- Participant-related delays: including hospitalisation, rehabilitation, custody, bereavement, or other extenuating personal circumstances.

Control

Participants will retain the same support as they would otherwise have received, including access to smaller personalised budgets or grants, as they would have had in the absence of the trial.

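### Protocol 10.6 names two-stage least squares for the CACE but prints a threshold first stage on allocation alone and a separate OLS, whose own standard error is not the 2SLS one (minor)

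*Protocol*

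**What the plan says.** Protocol section 10.6, under CACE Analysis, plans a complier average causal effect as a conditional sensitivity analysis: "For compliance levels lower than the specified threshold", it is to be estimated by the "instrumental variable (IV) approach with the two-stage least squares method".

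- **First stage.** The text introduces "treatment received by participants, specified by" d_i as being regressed on allocation B_i. The printed equation is d_i = 1{γ0 + γ1·B_i + e_i > 0}, with the note "Where 1{.} is an indicator function that is equal to 1 if its argument is true and 0 otherwise". No distribution is given for e_i, and no covariates appear.
- **Second stage.** The outcome is then regressed on E(d_i|B_i) "with an OLS regression of the form" Y_ipt = α + β1·Y_ip0 + β2·E(d_i|B_i) + β3·X_i + β4·P_p + u_i. The coefficient β2 is called the CACE estimator. No method is stated for its standard error.

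On receipt in the control arm, Table 5 (section 4.3) says "control participants will not be allocated a personalised budget but are entitled to all otherwise available support". Section 5.2, under Control, says controls keep their usual support, "including access to smaller personalised budgets or grants".

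**The concern.** Two-stage least squares has a linear first stage that contains every exogenous covariate of the outcome equation, and a standard error built from residuals that use actual receipt. The printed equations have neither feature. Two competent analysts could therefore follow the same page to different procedures: one would call a 2SLS routine, the other would fit a binary-response model and then an OLS by hand.

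The second analyst meets two problems. With no control recipients the binary-response fit breaks down, and the OLS output reports a standard error that does not belong to the named method. Section 10.6 records that some spending deviations were substantial, and version 2.0 was issued partly to clarify non-compliance, so this analysis may well be needed. The choice should not be left until results are visible.

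**Working it through.** **Inputs from the protocol.** Analysed N = 270 (9.2); baseline-endline correlation 0.6, two-sided alpha 0.05, power 0.8 and MDES 0.273 (9.1 and Table 7); 1:1 allocation stratified by partner (5.2); ten partners listed in Table 5; no budget allocated to controls (Table 5).

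**Assumed, because the protocol gives no values.** Uptake in the intervention arm 50, 70 or 90%; control receipt 0 or 10%; effect of receipt 0, 0.273 or 1.0 SD (1.0 SD with no control receipt only); correlation between uptake and outcome −0.5, 0 or 0.5.

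**1. The plan's own figure.** MDES = (z0.975 + z0.80) × √((1 − 0.6²) × 4/N) = 2.802 × √(2.56/N). This gives 0.236 at N = 360, 0.273 at N = 270 and 0.293 at N = 234, all matching Table 7. The protocol gives no figure for the CACE.

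**2. First stage fitted literally.** With 135 per arm and no control receipt, the probit fit fails with a singular matrix. The logit does not converge: its coefficients are about −34 and +35, with standard errors of about 2.7 million. The control arm is perfectly predicted, so no finite maximum-likelihood estimate exists. Software that drops perfectly predicted observations would leave only the intervention arm, where fitted receipt is constant and β2 is not identified.

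**3. What the second stage needs.** It needs only E(d|B). With one binary instrument this is the arm proportion under any link: E(d|B) = p0 + (p1 − p0)·B. At 60% uptake, both the linear fit and the limiting fitted values of the logit are 0 and 0.600. Substituting into the second stage, the coefficient on B equals β2·(p1 − p0), so β2 = adjusted ITT effect / (p1 − p0). Because B is randomised within partner, leaving covariates out of the first stage causes no material bias. In simulation (1,500 runs per setting), the 95th percentile of the absolute difference from full 2SLS was 0.001 to 0.008 SD at an effect of 0.273 SD.

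**4. The standard error.** The OLS residual is u + β2·(d − E(d|B)), whereas the 2SLS residual is u. The residual variance therefore changes by β2²·V + 2·β2·C, where V is the mean over arms of p(1 − p) and C is the covariance of u with d − E(d|B). With no selection (C = 0) and residual variance 1 − 0.6² = 0.64, the SE ratio is √(1 + β2²·V/0.64). Taking 90% uptake and no control receipt, V = 0.09/2 = 0.045:

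- effect 0.273: √(1 + 0.0745 × 0.045/0.64) = 1.003 (simulated 1.002)
- effect 1.0: √(1 + 0.045/0.64) = 1.035 (simulated 1.035)

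Selection adds the term in C, which can take either sign and vanishes when β2 = 0.

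**5. Simulation across all settings** (mean SE as written / mean 2SLS SE, and 95% interval coverage where computed):

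| Effect of receipt | SE ratio | Coverage as written | Coverage 2SLS |
|---|---|---|---|
| 0 | 0.991-1.000 | – | – |
| 0.273 SD | 0.953-1.048 | 93.5-96.8% | 93.9-96.5% |
| 1.0 SD | 0.969-1.199 | 93.5-98.5% | 94.1-95.8% |

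For example, at 70% uptake, 10% control receipt and an effect of 0.273 SD, the ratio is 1.048 or 0.959 depending on the sign of selection.

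**The case against.** The best defence is that the page can be read benignly. It never mentions probit or logit, gives e_i no distribution, says d_i is regressed on B_i, and names 2SLS. The indicator may simply describe binary take-up, and showing two stages with OLS second is a common way to present the method. An analyst who calls a standard 2SLS routine gets the right answer and the right standard error. Zero control receipt is also an expectation rather than a certainty: section 13.2 foresees non-adherence to randomisation, and if other budgets available to controls counted as receipt, the separation would disappear.

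Much of this stands, and it limits the point. A reader might infer that the first stage cannot be fitted at all. That does not follow: only the maximum-likelihood coefficients of a probit or logit fail, while E(d|B) stays defined and a linear fit is straightforward. A reader might also infer that the confidence interval is always too wide. It is not: the direction depends on selection. Nor is the CACE the only analysis that bears on receipt, since section 10.6 also plans a check that reclassifies non-compliant participants and refers to a per-protocol analysis.

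What the defence does not remove is the mismatch. The printed equations are not those of the named method, and OLS is the only estimation instruction given for the second stage.

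**Conclusion.** The equations in section 10.6 contradict the method it names and should be corrected, at minor severity. The CACE point estimate is sound. A binary-response first stage has no finite estimate under the expected zero control receipt, and the OLS step run by hand reports a standard error that is not the 2SLS one. For an effect of 0.273 SD that error is at most about 5%, in either direction. With no effect it is under 1%, so a test of no effect is essentially unaffected. It reaches about 20% only with a 1 SD effect and strong selection.

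These sizes rest on the assumed uptake, control receipt and selection listed above, with 0.273 SD taken as the effect of receiving a budget. If 0.273 SD were instead the intention-to-treat effect and no control received a budget, the complier effect would be 0.273/0.9 = 0.30 to 0.273/0.5 = 0.55 SD, and the error could be somewhat larger. The primary intention-to-treat analysis and the sample size do not change.

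**What to change.** Replace the indicator equation with a linear first stage that carries the covariates of the outcome equation:

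d_i = γ0 + γ1·B_i + γ2·Y_ip0 + γ3·X_i + γ4·P_p + e_i

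State that both stages are estimated together in one 2SLS routine and that its 2SLS standard errors are reported. Delete the indicator notation and the instruction to run a separate OLS. Robust standard errors are optional.

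The cost is a rewording of the two printed stages. No new data or additional analysis is needed, and no drawback is apparent.
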